4.4.2.2.5 Duration

Duration is derived from the start and end dates of the unsolicited AE:

End date of unsolicited AE - start date of unsolicited AE + 1.

The duration should be considered as missing only if one or both of the start and end dates of the unsolicited AE is missing or partially missing.

4.4.2.3 SAEs (including AESIs)

An event will be considered as a serious event if “Yes” is checked for “Serious” in the CRF. An event will be considered as an AESI if “Yes” is checked for “Is the event an AESI?” in the CRF.

SAEs (including AESIs) will be analyzed throughout the study using the following periods:

- Within 7 days (D0 to D7) after vaccination
- Within 30 days (D0 to D30) after vaccination
- During the study (i.e., all SAEs occurred during the study), including the 6-month follow-up period
- During the 6-month follow-up

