#### 6.1.2.3 Dose Selection and Timing

Subjects in Group 1 and Group 2 will receive MenACYW conjugate vaccine or MENVEO® at 2, 4, and 6 months of age.

Subjects in Group 2 will receive MENVEO® at 12 months of age.

### 6.1.3 Identity of Other Product 1

**Pentacel®:** (Diphtheria and Tetanus Toxoids and Acellular Pertussis Adsorbed, Inactivated Poliovirus and Haemophilus b Conjugate (Tetanus Toxoid Conjugate) Vaccine (Sanofi Pasteur Ltd, Toronto, Ontario, Canada)

**Form:** Liquid DTaP-IPV used to reconstitute lyophilized ActHIB®

**Dose:** 0.5 mL

**Route:** IM

**Batch number:** TBD

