3.1 Study Design

This study will be a Phase III, partially modified double-blind, randomized, parallel-group, active-controlled, multi-center study to compare the immunogenicity and safety of MenACYW conjugate vaccine and MENVEO® (Meningococcal [Groups A, C, Y, and W-135] Oligosaccharide Diphtheria CRM₁₉₇ Conjugate Vaccine) when administered concomitantly with routine pediatric vaccines to healthy infants and toddlers in the US.

Approximately 2628 healthy infants aged ≥ 42 to ≤ 89 days will be randomized 2:1 to the following 2 groups:

- **Group 1 (G1):** MenACYW conjugate vaccine and routine vaccines
- **Group 2 (G2):** MENVEO® and routine vaccines

Each group will be further randomized 2:1 in 2 subgroups based on the time of analyses conducted in the 2nd year of life (30 days after the 12-month vaccination or 30 days after the 15-month vaccination, respectively):

- **Group 1:**
 - **Subgroup 1a (G1a)** (12 months): MenACYW conjugate vaccine and routine vaccines at 2, 4, 6, and 12 to 15 months of age
 - **Subgroup 1b (G1b)** (15 months): MenACYW conjugate vaccine at 2, 4, 6, and 15 to 18 months of age and routine vaccines at 2, 4, 6, 12 to 15 months of age, and 15 to 18 months of age
- **Group 2:**
 - **Subgroup 2a (G2a)** (12 months): MENVEO® at 2, 4, 6, and 12 months of age and routine vaccines at 2, 4, 6, 12, and 15 to 18 months of age
 - **Subgroup 2b (G2b)** (15 months): MENVEO® at 2, 4, 6, and 12 months of age and routine vaccines at 2, 4, 6, 12, and 15 to 18 months of age

To be specific, the time of analyses as well as the collection of blood samples conducted in the 2nd year of life for Subgroup 1a and 2a is 30 days after the 12-month vaccination. The time for Subgroup 1b and 2b is 30 days after the 15-month vaccination. The schedule of vaccination and blood sampling is further detailed in [Table 3.1](#).

All subjects will receive the following routine vaccines as per the ACIP recommendations (see [Table 3.1](#)).

- Pentacel® (diphtheria, tetanus, pertussis [acellular, component]-poliovirus [inactivated]//*Haemophilus influenzae* type b [DTaP-IPV//Hib]) at 2, 4, 6, and 15 to 18^a months of age
- Prevnar 13® (pneumococcal 13-valent conjugate vaccine [PCV13]) at 2, 4, 6, and 12 to 15 months of age
- RotaTeq® (pentavalent rotavirus vaccine [RV5]) at 2, 4, and 6 months of age
- ENGERIX-B® (HB vaccine) at 2 and 6 months of age^b
- M-M-R® II (measles, mumps, rubella [MMR] vaccine) at 12 to 15 months of age

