- VARIVAX® (varicella vaccine) at 12 to 15 months of age

In addition, subjects in Subgroup 1b and Group 2 will receive the first dose of hepatitis A (HepA) vaccine (HAVRIX®) at 15 to 18 months of age as part of the study. For Subgroup 1a, there will be no HepA vaccination provided as part of the study. Subjects in Subgroup 1a should be vaccinated, as per standard practice, after the completion of the last study visit.

Blood sample for immunogenicity assessment will be assayed for meningococcal antibodies and for antibodies elicited in response to selected routine pediatric vaccines.

Safety data will be collected as follows: Immediate unsolicited systemic adverse events (AEs) will be collected within 30 minutes after each vaccination. Solicited-AE information will be collected from D0 to D07 after each vaccination; unsolicited-AE information will be collected from D0 to D30 after each vaccination; Serious adverse events (SAE) (including adverse events of special interest [AESIs]) and medically-attended-adverse-event (MAAE) information will be collected throughout the study from Visit 1 until the end of the 6-month follow-up period after the last vaccination.

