- All subjects will be followed for safety from Visit 1 to 6 months after the last vaccination.
- All subjects will be observed for 30 minutes after each vaccination, and any unsolicited systemic AEs occurring during that time will be recorded as immediate unsolicited systemic AEs in the electronic case report book (CRB).
- The subject's parent/guardian will record information in a diary card about solicited reactions from D0 to D07 after each vaccination and unsolicited AEs from D0 after each vaccination to the next study visit.
- SAEs and MAAEs will be recorded throughout the study. The subject's parent/guardian will record information in a diary card about SAEs and MAAEs from Visit (V) 01 to V02, from V02 to V03, from V03 to V04, from V04 to V05, from V05 to V06, from V06 to V07 (for Subgroups 1b, 2a, and 2b), and from V07 to V08 (for Subgroup 2a only). SAEs and MAAEs will also be recorded in a memory aid (MA) from D31 after the last vaccination visit, until the 6-month follow up phone call. The subject's parent/guardian will be asked to notify the site immediately about any potential SAE at any time during the study.
- Staff will contact the subject's parent/guardian by telephone 8 days (+2 days) after each vaccination visit to identify the occurrence of any SAEs (including AESIs) and/or MAAEs not yet reported and to remind them to complete the diary card and to bring it back at the subsequent visit.
- The completed diary cards will each be collected and reviewed with the subject's parent/guardian at the subsequent visit.
- Staff will contact the subject's parent/guardian by telephone within 14 days before V05 to remind them about the forthcoming study visit. If the subject's participation in the study is discontinued, the information recorded on the diary card will be reviewed at this time and the diary card will be retrieved by the site.
- Staff will contact the subject's parent/ guardian by telephone at 6 months (+30 days) after the last vaccination visit to review the MA and identify the occurrence of any MAAEs and SAEs (including AESIs) that have not been reported.

Table 3.3: Study procedures for infant vaccination (aged 2 months to 7 months)

Visit / Contact	Visit 1	Telephone Call (TC) 1*	Visit 2	TC 2*	Visit 3†	TC 3*	Visit 4
Approximate age of subjects	2 months (42 – 89 days)	--	4 months	--	6 months (164 – 224 days)	--	7 months

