Immediate surveillance (30 min)	X		X		X					X		X		X		
Diary card (DC) provided	DC1		DC2		DC3		DC4		DC5		DC6		DC7			
Telephone call		X		X		X		X		X		X		X		

Visit / Contact	Visit 1	Telephone contact (TC)1*	Visit 2	TC2*	Visit 3	TC3*	Visit 4	TC4†	Visit 5‡	TC5*	Visit 6	Visit7§	TC6*	Visit 8	TC7**	Follow-up Contact
Diary card reviewed and collected			DC1		DC2		DC3		DC4		DC5	DC6		DC7		
Recording of solicited injection site and systemic AEs	X		X		X				X			X				
Recording of unsolicited AEs																
Collected from D0 to D30 after each vaccination																
Reporting of serious adverse events (SAEs, including AESIs) and medically-attended AEs (MAAEs)****																
To be reported throughout the study																
Collection of reportable concomitant medications	X		X		X		X		X		X	X	X	X	X	
Memory aid (MA) provided††††															MA	
Trial termination record (termination of active portion of the trial)														X		

IRT: interactive response technology

*This call is made 8 days after the respective vaccinations. If day 8 falls on a weekend or holiday, the telephone call may be made on the following business day. During this telephone call, the staff will find out whether the subject experienced any SAE (including AESI) and/or MAAE not yet reported and will remind the subject's parent/guardian to continue using the diary card to bring the diary card to the study center at the next visit, and confirm the date and time of the next visit.

†Staff will contact the subject's parent/ guardian by telephone within 14 days before V05 to remind them about the forthcoming study visit. If the subject's participation in the study is discontinued, the information recorded on the diary card will be reviewed at this time and the diary card will be retrieved by the site.

‡At V05, subjects must be 12 months of age (from the day subjects become 12 months old until the day before becoming 13 months old).

§At V07, Subjects must be between 15 and 18 months of age (from the day subjects become 15 months until the day before becoming 19 months of age).

**Staff will contact the subject's parent/ guardian by telephone at 6 months (+ 30 days) after the last vaccination visit to identify the occurrence of any SAEs (including any AESIs) and medically-attended AEs not yet reported. The final telephone call will continue until contact is made or 28 days have passed at which time the subject will be considered lost to follow-up.

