5.1.4.1 Statistical Methods

Safety

Safety results will be described for subjects in all study groups. The main parameters for the safety endpoints will be described by 95% Cis using the exact binomial method (Clopper-Pearson method) (15).

Safety analyses will contain at least the descriptions listed in [Table 5.5](#):

Table 5.5: Statistical analyses for safety observational objectives

Safety Events	Time and Group	Description
Immediate unsolicited non-serious systemic AE	Within 30 minutes after each vaccination in Group 1 and Group 2	Proportion of subjects that have the event, MedDRA terms, intensity, relationship to vaccine, study discontinuation, duration
Solicited injection site reactions	D0 to D7 after each vaccination in Group 1 and Group 2	Proportion of subjects that have the event, time of onset, duration, intensity, action taken, study discontinuation, number of days of occurrence, temperature collection routes
Solicited systemic reactions		
Unsolicited non-serious AE/AR	D0 to D30 after each vaccination in Group 1 and Group 2	Proportion of subjects that have the event, MedDRA terms, time of onset, duration, intensity, relationship, action taken, study discontinuation
AEs leading to study discontinuation	D0 to D30 after each vaccination in Group 1 and Group 2; D31 to next visit after each vaccination in Group1 and Group2;	Proportion of subjects that have the event, MedDRA terms, time of onset, duration, intensity, relationship,

Safety Events	Time and Group	Description
	During the whole study in Group 1 and Group 2	action taken, study discontinuation
MAAE	D0 to D30 after each vaccination in Group 1 and Group 2; D31 to next visit after each vaccination in Group1 and Group2; During the whole study in Group 1 and Group 2	Proportion of subjects that have the event, MedDRA terms, onset, duration, intensity, relationship, action taken, study discontinuation
SAE (including AESI)	D0 to D7 after each vaccination in Group1 and Group 2; D0 to D30 after each vaccination in Group1 and Group 2; D31 to next visit after each vaccination in Group1 and Group2; During the whole study in Group1 and Group 2	Proportion of subjects that have the event, MedDRA terms, onset, duration, relationship, seriousness criteria, outcome, study discontinuation

Note: “Group1 and Group2” mentioned in the above table 5.5 for safety analyses also includes the Subgroup 1a, Subgroup 1b, Subgroup 2a and Subgroup 2b, when it is applicable.

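### The SAP's six-month follow-up row for SAEs and AESIs runs from the last study vaccination visit, so it is not aligned on the fourth meningococcal dose between Group 1 and Group 2

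*SAP*

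**What the plan says.** SAP 4.4.2.3 gives four periods for SAEs including AESIs: D0 to D7, D0 to D30, the whole study, and "During the 6-month follow-up". The last has no start day and no reference dose. SAP Table 5.5 (section 5.1.4.1) does not list it. That table has D0 to D7, D0 to D30, "D31 to next visit after each vaccination in Group1 and Group2", and the whole study.

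The anchor has to be read from the study plan. SAP 3.1 collects SAEs and MAAEs "throughout the study from Visit 1 until the end of the 6-month follow-up period after the last vaccination". SAP 3.2 places the final contact "by telephone at 6 months (+30 days) after the last vaccination visit". On diary recording after the active phase, the same section states: "SAEs and MAAEs will also be recorded in a memory aid (MA) from D31 after the last vaccination visit, until the 6-month follow up phone" (that is, up to the final contact).

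The fourth meningococcal dose sits differently in the two schedules. In Group 1 the last study vaccination visit is the MenACYW dose 4 visit. Both Group 2 subgroups receive "MENVEO® at 2, 4, 6, and 12 months of age and routine vaccines at 2, 4, 6, 12, and 15 to 18 months of age" (SAP 3.1), and Protocol 6.1.2.3 confirms that "Subjects in Group 2 will receive MENVEO® at 12 months of age". Their last study vaccination visit gives Pentacel and HAVRIX only. For Subgroup 2a the footnote to SAP Table 3.6 reads "At V07, Subjects must be between 15 and 18 months of age (from the day subjects become 15 months until the day before becoming 19" (ages counted in months); for 2b the same age window applies at Visit 6 (Table 3.7).

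**The concern.** SAEs and AESIs (generalized seizures, Kawasaki disease, Guillain-Barré syndrome, ITP) are the long-term safety outcomes of the trial. A row headed with the six-month follow-up and set out by group will be read as the months after the fourth meningococcal dose. That reading fits Group 1. In Group 2 the row holds the months after two routine vaccines, and part or all of the first six months after MENVEO dose 4 lies before it begins. A difference between groups in this row, or the absence of one, could reflect time since dose or age rather than the meningococcal vaccine. No other listed period gives a common six-month window after dose 4.

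**Working it through.** **Check of the anchor against the plan's own figures.** Duration = age at last study vaccination visit + 6 months − 2 months (age at entry).
- Subgroup 1a: 12 + 6 − 2 = 16 and 15 + 6 − 2 = 19 months. The Protocol Synopsis states 16 to 19.
- Subgroup 1b and Group 2: 15 + 6 − 2 = 19 and 18 + 6 − 2 = 22 months. The Synopsis states 19 to 22.

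Both agree, so the follow-up does run from the last study vaccination visit. The call schedule in Protocol 5.1.4.2 confirms it: 180 (+30) days after Visit 5 in 1a, Visit 6 in 1b, Visit 7 in 2a and Visit 6 in 2b.

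**Offset from the fourth meningococcal dose.**
- Group 1: 0 days, because dose 4 is given at the anchor visit.
- Group 2: MENVEO dose 4 falls from 12 months to the day before 13 months, and the last vaccination visit from 15 months to the day before 19 months (SAP Tables 3.6 and 3.7). With 30.4375 days per month:
  - shortest: 15 × 30.4375 − (13 × 30.4375 − 1) = 61.9, about 62 days (2.0 months)
  - longest: (19 × 30.4375 − 1) − 12 × 30.4375 = 212.1, about 212 days (7.0 months)

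Ignoring the one-day edges gives 2 × 30.4375 = 61 and 7 × 30.4375 = 213 days.

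**What the Group 2 row covers,** in days after MENVEO dose 4. Overlap with the first 180 days = max(0, 180 − start of row).

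| Gap (days) | Row if it starts at D0 after last vaccination | Overlap | Start if at D31 | Overlap |
|---|---|---|---|---|
| 62 (shortest) | 62 to 242 | 118 | 93 | 87 |
| 91 (3 months) | 91 to 271 | 89 | 122 | 58 |
| 183 (6 months) | 183 to 363 | 0 | 214 | 0 |
| 212 (longest) | 212 to 392 | 0 | 243 | 0 |

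Even at the shortest gap, 62/180 = 34% of the first 180 days after MENVEO dose 4 precedes the row. In Group 1 the row starts at day 0 or day 31 after MenACYW dose 4. The difference between groups is the same under either start: 93 − 31 = 62 and 243 − 31 = 212 days.

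**Whether another listed period fills the gap.**
- D0 to D7 and D0 to D30 are too short.
- The day-31-to-next-visit period works in 2b, where the next visit after MENVEO dose 4 is the Pentacel/HAVRIX visit itself. In 2a the next visit is Visit 6, at day 30 to 51. The stretch from Visit 6 to Visit 7 lasts from 62 − 51 = 11 days to 212 − 30 = 182 days and falls in no period except the whole study. Subgroup 2a is 584 of the 876 planned Group 2 children.
- The whole-study period holds every event but does not align time since dose 4.

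**Whether the data allow an aligned window.** SAEs are recorded continuously from Visit 1. Group 2 is scheduled to be followed to at least 62 + 180 = 242 days after MENVEO dose 4, and Group 1 to at least day 180 after MenACYW dose 4. D0 to D180 after dose 4 is therefore available in every subgroup.

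**The case against.** The strongest reply is that nothing planned is invalidated. SAP 5.1.4 tests no safety hypothesis, SAP 2.3 sets out only to describe the safety profile, and no between-group safety difference is specified. Every SAE and AESI after MENVEO dose 4 is in the whole-study summary. Table 5.5 does not list this period, so no between-group use of it is laid down. Its note allows results by subgroup, and 1b, 2a and 2b share the same age window for the last vaccination visit. All of this stands, and it limits the weight of the point. It does not align the row: 2a and 2b are both offset, so subgroup display alone does not help. SAP 3.1 also describes the study as comparing safety as well as immunogenicity, so readers will set the two columns side by side.

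The reply is also right that an aligned window moves some differences rather than removing them. Subgroup 1b starts at an older age with Pentacel and HAVRIX on day 0; Group 2 will often have that visit inside the window; 1a may receive its off-study Pentacel there.

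Three stronger readings are tempting but unsupported. One is that late events after MENVEO dose 4 are lost; they are absent from this row only. Another is that the row captures everything after MenACYW dose 4. The start day is undefined, and the memory-aid text (D31) or Protocol 11.1 (from the last study visit) would leave out about the first month. The third is a single figure for the share of post-dose time missed in Group 2. An average near 75% comes from assuming visit ages uniform within their windows and is a share of time, not of events.

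**Conclusion.** The point holds as a matter of definition and alignment within a descriptive analysis. The six-month follow-up row starts about 2 to 7 months later, relative to the fourth meningococcal dose, in Group 2 than in Group 1. Depending on the child's visit dates and a start at D0, it shares between 118 and 0 days with the 180 days after MENVEO dose 4. This rests only on the stated visit windows and on reading the period from the study plan, since SAP 4.4.2.3 does not define it. The offset does not depend on whether the period starts at D0 or D31. The reporting gap outside the whole-study summary is confined to 2a, between Visit 6 and Visit 7. The documents do not support saying that the safety analysis is invalid or incomplete. They do support saying that this row should not be used to compare the two meningococcal vaccines, and that an aligned summary can be made from data already collected.

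**What to change.** 1. In SAP 4.4.2.3, state the start day of the six-month follow-up period. Label it as running from the last study vaccination visit and not aligned on the fourth meningococcal dose between groups. Reconcile it with Table 5.5, either by listing it there or by removing it from 4.4.2.3.
2. Alongside it, add one descriptive SAE/AESI summary for D0 to D180, and D31 to D180, after the fourth dose of MenACYW or MENVEO. Count from Visit 5 in 1a, 2a and 2b and from Visit 6 in 1b. Show it by subgroup, with 1a against 2a as the closest comparison.
3. Footnote what remains different: the Group 2 window contains the Pentacel/HAVRIX visit whenever the gap is 180 days or less, which is most of the permitted range; 1b receives those vaccines on day 0 and at an older age; 1a may receive off-study Pentacel within the window.

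The cost is SAP wording, one extra table and its footnotes. No visit, contact or data item changes.

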4.4.2.4 Medically-Attended Adverse Event (MAAE)

An event will be considered as a MAAE if “Yes” is checked for “Is the event an MAAE?” in the CRF.

MAAE will be analyzed during the following time periods:

- Within 7 days after vaccination
- Within 30 days after vaccination
- During the study (i.e., all MAAEs occurred during the study), including the 6-month follow-up period.

4.4.2.5 Other Safety Endpoints

4.4.2.5.1 Action Taken

This information will be summarized as collected, including missing observations. No derivation or imputation will be done.

4.4.2.5.2 Seriousness

This information will be summarized as collected. No derivation or imputation will be done.

4.4.2.5.3 Outcome

This information will be summarized as collected. No derivation or imputation will be done.

4.4.2.5.4 Causality

This information will be summarized as collected in the field “Relationship to Investigational Product”. Missing causal relationship will be handled as described in [Section 5.4.1.2](#). Relationship to study procedure is only presented in the listing.

4.4.2.5.5 AEs Leading to Study Discontinuation

This information will be summarized as collected. A flag is available in the clinical database for all AEs in order to identify AEs leading to Discontinuation.

In general, the items that are counted are:

- Disposition table: A subject who on the “Completion at End of Study” form
- Question “What was the participant's status?” has “Adverse Event” checked.
- Safety overview table: A subject who either on the “Completion at End of Study” form, question “What was the participant's status?” has “Adverse Event” checked or lists a solicited AE that has “Caused Study Termination” checked that is at least Grade 1 or an unsolicited AE that has “Caused Study Discontinuation” checked that is at least Grade 1 or missing and is within the time period indicated.
- System Organ Class/Preferred Term (SOC/PT) table: A solicited AE that has “Caused Study Termination” checked that is at least Grade 1 or an unsolicited AE that has “Caused Study Discontinuation” checked that is at least Grade 1 or missing and is within the time period indicated.

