### 5.2.8 Conditions for Withdrawal

Parents / guardians will be informed that they have the right to withdraw their child from the study at any time.

A subject may be withdrawn from the study:

- At the discretion of the Investigator or Sponsor due to safety concerns or significant non-compliance with the protocol (based on the Investigator's judgment), without the subject's permission (withdrawal)
- At the request of the parent / guardian (dropout)

The reason for a withdrawal or dropout should be clearly documented in the source documents and on the CRB.

The Investigator must determine whether voluntary withdrawal is due to safety concerns (in which case, the reason for discontinuation will be noted as "Adverse Event") or for another reason.

Withdrawn subjects will not be replaced.

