5.1.5.2 Subgroup Analysis by Race and Gender

Subgroup analyses by gender and race for will be provided in Appendix 15 of the CSR.

The gender subgroup analyses will have two categories (Female and Male), and the race subgroup analyses will have four categories (White, Black, Asian, and Other).

For primary and secondary immune responses after meningococcal vaccinations, these subgroup analyses will be conducted between Group 1 and Group 2 as well as between Subgroup 1a and 2a by gender and race.

For safety responses, these subgroup analyses will be mostly performed between Group 1 and Group 2 by gender and race.

Immunogenicity analyses

The followings are the serological endpoints will be assessed by gender and race:

- 1) hSBA vaccine seroresponse to meningococcal serogroups A, C, Y, and W assessed before first study vaccination on D0 and 30 days after the 4th meningococcal vaccination (Subgroup 1a vs Subgroup 2a).
- 2) Antibody titers $\geq 1:8$ against meningococcal serogroups A, C, Y, and W measured by hSBA assessed 30 days after vaccinations at 6 months of age (Group 1 vs Group 2).
- 3) The following serological endpoints will be assessed (including effect of 4th dose of MenACYW or Menveo):
 - Before the 12-month vaccination (pre-4th dose) for Subgroups 1a and 2a
 - hSBA meningococcal serogroups A, C, Y and W antibody titers
 - 30 days after the 12-month vaccination for Subgroups 1a and 2a
 - hSBA meningococcal serogroups A, C, Y and W antibody titers
 - Percentage of subjects with titer ≥ 4 -fold rise form pre-dose 4 vaccination to post-dose 4 vaccination and 95%CI
- 4) The following serological endpoints will be assessed (persistence of bactericidal antibodies after infant vaccination with MenACYW or Menveo):
 - 30 days after the 6-month vaccination and before the 12-month vaccination for Subgroup 1a and Subgroup 2a
 - hSBA meningococcal serogroups A, C, Y, and W antibody titers
 - GMTs with 95% CI
 - Percentage of subjects with titer $\geq 1:4$ and $\geq 1:8$ and 95% CI

Safety analyses

Safety overview after any vaccine injection by gender– Overall Safety Analysis Set

Safety overview after vaccine injections at 2 months of age by gender – Safety Analysis Set 1

Safety overview after vaccine injections at 4 months of age by gender – Safety Analysis Set 2

Safety overview after vaccine injections at 6 months of age by gender – Safety Analysis Set 3

Safety overview after vaccine injections at 12 months of age by gender – Safety Analysis Set 4

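### The completion-form condition for AEs leading to discontinuation (SAP 4.4.2.5.5) has no dose or time limit, so one AE dropout can be counted in several per-dose safety overviews

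*SAP*

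**What the plan says.** SAP 4.4.2.5.5 sets three counting rules for AEs leading to discontinuation.

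- **Disposition table.** A child counts if the end-of-study form gives 'Adverse Event' as the status.
- **Safety overview.** The rule starts "Safety overview table: A subject who either on the “Completion at End of Study” form" and goes on "question “What was the participant's status?” has “Adverse Event” checked or lists a solicited AE". It offers three alternatives: the form status; a solicited AE flagged as causing termination; or an unsolicited AE flagged as causing discontinuation. The sentence ends with the qualifier "checked that is at least Grade 1 or missing and is within the time period indicated".
- **SOC/PT table.** The rule starts "System Organ Class/Preferred Term (SOC/PT) table: A solicited AE that has “Caused Study Termination” checked" and uses AE records only. The form status plays no part.

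The overviews are listed by dose in SAP 5.1.5.2 and 5.1.5.3, for example "Safety overview after vaccine injections at 2 months of age by gender – Safety Analysis Set 1". There is one for each of SafAS1 to SafAS5, plus an overall and an all-four-dose version. SAP Table 5.5 plans AEs leading to discontinuation by period: "D0 to D30 after each vaccination in Group 1 and Group 2", then day 31 to the next visit, then the whole study.

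Protocol 5.2.10 has the site record a single most significant reason for early termination. Protocol 5.2.8 adds that "The Investigator must determine whether voluntary withdrawal is due to safety concerns"; if it is, the reason is noted as 'Adverse Event'.

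**The concern.** A per-dose overview should show what followed that dose. A flagged AE can be placed, because a solicited reaction is recorded against a vaccination and an unsolicited AE is assigned to the last vaccination by SAP 4.4.2.2.3. The form status is one entry for the whole study, and no rule assigns it to a dose. If it suffices on its own in every per-dose overview, the row becomes a whole-study count restricted to children who received that dose.

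The row is a tolerability summary that readers compare across doses and between vaccines. The excess falls on the early doses, because children who leave later have already entered the earlier sets. The same overviews feed the preterm and full-term analyses that SAP 5.8 says were added after communication with CBER.

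**Working it through.** The plan gives no figure to reproduce, so the check applies the written rule to the sets as defined.

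**Inputs**

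- SAP 5.2.3.2 to 5.2.3.6: a child enters the set for each dose visit at which a study vaccine was received and any safety data exist. The sets overlap.
- SAP 5.2.1 (footnote): study vaccine includes the routine vaccines. Subgroup 1b therefore enters SafAS4 at Visit 5, and Group 2 enters SafAS5 at 15 to 18 months, although neither receives a meningococcal vaccine at that visit.
- SAP Tables 3.4 to 3.7: 4 vaccination visits in Subgroup 1a; 5 in Subgroups 1b, 2a and 2b.
- SAP 4.4.2.2.3: the last-vaccination rule covers unsolicited AEs only.
- Protocol synopsis: 1168 children planned in Subgroup 1a, 876 in Group 2.

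**One child.** A child who leaves for an AE after visit k belongs to up to k per-dose sets. The form status is true in each, so the child is counted up to k times. An AE after the 6-month dose puts the child in the 2-, 4- and 6-month overviews: 3 tables where 1 is right. The maximum is k = 4 in Subgroup 1a and k = 5 elsewhere.

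**A group.** Let d_j be the number of AE dropouts after visit j, for j = 1 to K, with every child in the sets for the visits attended.

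- Literal count in the overview for dose i: d_i + d_(i+1) + … + d_K.
- Count attributable to dose i: at most d_i.
- Literal total over all per-dose overviews: 1·d_1 + 2·d_2 + … + K·d_K, against at most d_1 + … + d_K.

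The ratio of totals depends on timing alone. It is 1 if every child leaves after the first visit and K if every child leaves after the last.

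**Illustration only.** Assume one AE dropout after each vaccination visit and no other attrition.

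| | Subgroup 1a (K = 4, n = 1168) | Group 2 (K = 5, n = 876) |
|---|---|---|
| AE dropouts | 4 | 5 |
| Literal entries, all per-dose tables | 4+3+2+1 = 10 | 5+4+3+2+1 = 15 |
| 2-month row, literal | 4/1168 = 0.34% | 5/876 = 0.57% |
| 2-month row, by onset | 1/1168 = 0.09% | 1/876 = 0.11% |

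**After the fix.** Each child with a flagged AE appears in at most one per-dose overview, and still once in the any-dose overview.

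**Comparison with the SOC/PT rule.** That rule drops the form status. For a given dose, the overview can include children who are absent from the SOC/PT table: those whose flagged AE followed a later dose, and any with the status but no flagged AE.

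**The case against.** The strongest reply is that the closing time qualifier was meant to govern all three alternatives, so that the form status counts only in the matching period. The section also opens its list with 'In general', no table shell is given, and SAP 5.8 refers to standard safety tables that are not in the documents. The programmed table may therefore behave sensibly. SAP 4.4.3.3 shows that a termination-form date exists, so a child could in principle be placed by that date.

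Part of this stands. The SAP does not state that it will count one dropout several times; that follows from applying the rule as worded. But the qualifier attaches grammatically to the unsolicited-AE alternative, and the section does not say which date would place a form status in a period. A termination date is not an AE onset, and no rule uses it here. If the wider reading is intended, one clarifying sentence is still needed.

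Several stronger readings are tempting but unsupported:

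- *The two tables will disagree.* They can. They need not if few children leave for an AE or all leave after the first dose.
- *There is a fixed inflation factor.* With dropouts spread evenly over four visits, each would enter (1+2+3+4)/4 = 2.5 tables and the 2-month row would be 4 times too high. The even spread is an assumption, and no dropout rate is given.
- *The dose is hidden altogether.* Table 5.5 and the SOC/PT rule still report flagged AEs by period.
- *The form-status child certainly sits in a D0 to D30 row.* Table 5.5 plans three periods, but no passage fixes the period of the overview row.
- *Protocol 5.2.8 describes withdrawals with no flagged AE.* It says how safety-related withdrawals are classified and does not mention AE flags. An unflagged child is possible but not described.

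**Conclusion.** The point holds as a defect of wording that yields wrong per-dose figures if followed. The form-status alternative has no dose or period condition, while the overviews are per dose on overlapping sets. One AE dropout can enter up to 4 per-dose overviews in Subgroup 1a and up to 5 in Subgroups 1b, 2a and 2b, with the excess on earlier doses. This rests on the literal reading of SAP 4.4.2.5.5 and on the child having some safety data at each dose visit.

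The consequence is limited. Safety is descriptive (SAP 5.1.4), so no test, margin or primary result changes. The any-dose overview counts each child once, and the disposition table is right to use the form. The absolute size cannot be given, because the documents do not state how many children leave for an AE. The correction should be made because it is small and removes a conflict with Table 5.5 and with the SOC/PT rule in the same section.

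**What to change.** Amend SAP 4.4.2.5.5 as follows.

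1. In the per-dose overviews (SafAS1 to SafAS5), count a child only if an AE flagged as causing discontinuation or termination had its onset after that dose and within the table's stated period. Use the last-vaccination rule of SAP 4.4.2.2.3 for unsolicited AEs.
2. Use the form status on its own only in the disposition table and in the any-dose, whole-study overview.
3. Footnote or list children whose status is 'Adverse Event' but who have no flagged AE.

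The cost is a wording change and one derivation. SAP 4.4.2.5.5 says the discontinuation flag is held for all AEs, so no new data are needed. The small downside is that children without a flagged AE will not appear in any per-dose row. The footnote or listing keeps them visible, and they remain in the disposition table and the any-dose overview.
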